Evidence suggests that culturally-tailored interventions may increase cessation in AIs but face-to-face delivery is costly and hindered by lack of transportation among participants. Prior work by the American Indian Cancer Foundation (AICAF; subcontract on proposal), shows that references to traditional tobacco in cessation messages can positively affect self-efficacy to quit (unpublished data). To our knowledge, only two culturally-tailored cessation interventions for AI peoples exist that purposely engage AI voices throughout the research and utilized rigorous methodology (i.e., included a control group, biochemically confirmed abstinence). The first is the All Nations Breath of Life (ANBL) intervention which was created for AIs representing many tribes and included pharmacotherapy, in-person behavioral support led by AI facilitators, and culturally-tailored curriculum.¹⁰ Biochemically confirmed abstinence was higher in the tailored versus standard group, though the difference between the groups was not statistically significant (11% vs 7%).¹⁰ The second, a tribal-specific program which included pharmacotherapy, also observed higher, but non-significant, abstinence in the tailored versus standard group (23% vs 14%).¹¹ Both studies observed poor retention (~40% loss-to-follow-up) and lack of transportation was a major contributor. Innovative approaches that can reach AI smokers and, that overcome the barrier of travel to an intervention site are needed to address commercial smoking among AI people.

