12.0 Withdrawal of Participants

12.1 Withdrawal Circumstances:

Participants can choose to withdraw themselves at any time for any reason. Participants may be withdrawn by the PI if they no longer meet eligibility criteria.

12.2 Withdrawal Procedures:

If a participant is withdrawn, they will be informed and data collection will stop. All data or specimens collected up to that point will continue to be used. Compensation to that point will be provided.

MEDICAL PROTOCOL (HRP-590)

PROTOCOL TITLE: QuitGuide for American Indians: Aims 2 & 3

VERSION DATE: 11-16-2022

12.3 Termination Procedures:

If a participant is no longer eligible, they will be informed and data collection will stop. All data or specimens collected up to that point will continue to be used.

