15.0 Statistical Considerations

15.1 Data Analysis Plan:

No blinding of the investigative team will occur.

General Approach

All statistical analyses will be performed using SAS (version 9.4) or R (latest version, R Core Team). All statistical tests will be two-sided and a significance level of 0.05 will be used. Proper transformation such as the logarithm transformation will be used to approximate normality for

MEDICAL PROTOCOL (HRP-590)

PROTOCOL TITLE: QuitGuide for American Indians: Aims 2 & 3

VERSION DATE: 11-16-2022

the outcome variables. All analyses will be completed using intent-to-treat principle unless otherwise noted.

Describing the Study Population

Baseline characteristics will be summarized for all participants and by study arm to identify any treatment group imbalances post-randomization. This will include household income, education level, traditional tobacco use, cultural identity, multiple tobacco use, quit readiness, nicotine dependence and CPD. Continuous variables will be summarized using mean, standard deviation, median and range, and compared between study arms using Student's t-tests or Wilcoxon rank-sum tests, as appropriate. Categorical variables will be summarized using frequency and percentage, and compared between study arms using Chi-square or Fisher's exact tests, as appropriate.

Primary Endpoint Analysis

The primary endpoint is the frequency of app use initiated by the participant. The number of times the app is initiated per day will be measured using data from Smokefree.gov. If a participant does not use the app on a particular day, Smokefree.gov records this as non-use or 0 for that day. The total number of times will be summarized for analysis by totaling the number of times the app is initiated from randomization to 5 weeks post-randomization.

Primary Analysis

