The objective of our primary analysis is to test the treatment effect on frequency of app initiated by the participant. Frequency of app initiated will be summarized by treatment group (tailored app vs standard app) using descriptive statistics, and analyzed using a Poisson regression model with covariates for treatment group and the three stratification factors (rural/urban clinic, male/female gender and <50 years of age/50+ years of age). Assumptions about mean and variance will be evaluated and if over-dispersion is present, negative binomial regression will be used. If data are zero-inflated, zero-inflated Poisson or negative binomial models may be considered.. This analysis will be performed using data for all participants who were randomized, while assuming non-use of app for those who did not complete the week 5 survey from the last day they launched the app.

Secondary Analysis

A secondary analysis of the primary endpoint will be performed that also adjusts for any other covariates that differ across treatment groups at baseline with a p-value less than 0.20 (covariates listed above). We acknowledge the limitations of this due to a small sample size and will take this into account when determining what additional covariates to adjust for. Additionally, a sensitivity analysis will be performed for all subjects who completed the week 5 survey.

Secondary and Exploratory Endpoint Analysis

Secondary and exploratory endpoints will be analyzed using the same approach as the primary endpoint. These endpoints will be analyzed using an appropriate regression framework (i.e. linear, logistic, Poisson etc.), adjusting only for baseline measurements of the endpoint, if available, and the three stratification factors (rural/urban clinic, male/female gender and <50 years of age/50+ years of age). Secondary analyses will consist of an adjusted analysis, as

MEDICAL PROTOCOL (HRP-590)

PROTOCOL TITLE: QuitGuide for American Indians: Aims 2 & 3

VERSION DATE: 11-16-2022

described above. All analyses will utilize residual plots and other diagnostic statistics to evaluate all modeling assumptions.

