Our sample size is based on the primary outcome, frequency of app use initiated by the participant during the 5-week period. Using a two-sided, two-sample test for Poisson rates, a total of 116 participants (n=58 in the tailored group and n=58 in the non-tailored group) will allow us to achieve 80% power to detect a difference in frequency of app use between the groups of 3.15 assuming a rate of 35 (1 time per day over the 5 weeks) in the non-tailored group and an alpha of 0.05. This sample size is in alignment with other mHEALTH-related smoking cessation feasibility studies.^{36, 50}

15.3 Statistical Analysis:

See above.

MEDICAL PROTOCOL (HRP-590)

PROTOCOL TITLE: QuitGuide for American Indians: Aims 2 & 3

VERSION DATE: 11-16-2022

15.4 Data Integrity:

PI will periodically check for completeness as well as outliers or unusual values

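### The only dropout-related sensitivity analysis of the primary endpoint keeps week-5 survey completers, although launches are logged without the survey; it drops observed totals and does not test unlogged days

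*Combined protocol and SAP*

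**What the plan says.** Section 15.1 (Primary Endpoint Analysis) takes daily launches from Smokefree.gov and sums them from randomisation to five weeks. Days without use are data, not gaps: "If a participant does not use the app on a particular day, Smokefree.gov records this as non-use or 0 for that day".

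The Primary Analysis includes everyone randomised, "assuming non-use of app for those who did not complete the week 5 survey from the last day they launched the app". Under Secondary Analysis comes the one check that touches on dropout: "Additionally, a sensitivity analysis will be performed for all subjects who completed the week 5 survey". The covariate-adjusted analysis in the same paragraph does not address missing data. Under Missing Data, multiple imputation is optional and limited to secondary and exploratory endpoints. The same subsection commits to using all observed data and assumes missingness at random.

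The exit survey is a separate REDCap link sent by email for self-reported outcomes (Section 5.2). On withdrawal, Section 12.2 says: "If a participant is withdrawn, they will be informed and data collection will stop". It does not say whether transfer of the app log stops as well.

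**The concern.** Skipping an emailed survey removes no launch data, so survey completion is the wrong marker of whether the primary endpoint is known. Two things follow.

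First, the survey condition in the primary analysis does nothing for a participant with a full log, since no launch can follow the last launch. It changes the data only if the log itself ends early, and then it enters zeros for days nobody observed. Conversely, it gives no rule for a survey completer whose log is incomplete.

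Second, the completer analysis discards observed totals, which sits badly with the plan's own commitment to use all observed data. Completing the survey happens after randomisation and may depend on how engaged a participant is and on which app was assigned. Section 1.1 hypothesises better acceptability for the tailored app, so a difference in completion is plausible. Agreement or disagreement between this analysis and the primary one would then say little about robustness, while the assumption about unlogged days is never varied.

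**Working it through.** **1. The plan's own power figure.** Inputs from Sections 15.1 and 15.2: two-sided alpha 0.05, 58 per arm, rate 35 in the standard arm, difference 3.15 (so 38.15 in the tailored arm), Poisson variance.

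- Power = Φ(3.15 / √((35 + 38.15)/58) − 1.96) = Φ(3.15/1.123 − 1.96) = Φ(0.845) = 0.801.
- n per arm = (1.96 + 0.8416)² × 73.15 / 3.15² = 57.9, so 58.

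The stated 80% with 116 participants is reproduced. It contains no allowance for loss, and needs none if every logged total is used.

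**2. The non-use rule with full logs.** Setting days after the last launch to zero cannot alter a log that already holds zeros there. Applied to 116 simulated 35-day logs, the rule changed 0 totals.

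**3. Precision of the completer analysis.** Same formula with n = 58 × (1 − non-completion). The protocol gives no expected non-completion for this trial, so 10% to 50% is an assumed range.

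| Non-completion | n per arm | Power for 3.15 | Difference detectable with 80% power |
|---|---|---|---|
| 0% | 58 | 80.1% | 3.15 |
| 10% | 52.2 | 75.8% | 3.32 |
| 20% | 46.4 | 70.8% | 3.52 |
| 30% | 40.6 | 65.1% | 3.76 |
| 40% | 34.8 | 58.4% | 4.06 |
| 50% | 29.0 | 50.9% | 4.45 |

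**4. When bias between arms arises.** All figures in this step are assumptions. Hand example: both arms truly average 35.

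- Standard arm: 60% complete (mean 45) and 40% do not (mean 20). Overall 0.6 × 45 + 0.4 × 20 = 35.
- Tailored arm: 70% complete, the extra 10 points all being low users (mean 20). Completer mean (60 × 45 + 10 × 20)/70 = 41.4. Overall 0.7 × 41.4 + 0.3 × 20 = 35.
- Completer difference 41.4 − 45 = −3.6, with a true difference of 0.

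Simulation: negative binomial counts with mean 35 in both arms and shape 1 or 2; the log-odds of completion rise by 1 per SD of log use unless stated.

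| Completion, standard vs tailored | Completer difference (true value 0) |
|---|---|
| 60% vs 60%, same link to use | 0.0 (both completer means about 42 to 45) |
| 60% vs 80% | −3.7 to −5.0 |
| 70% vs 85% | −2.8 to −3.6 |
| 60% vs 60%, weaker link in tailored arm (0.3 per SD) | −4.9 to −6.3 |

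The all-randomised difference stayed within simulation error of 0 throughout.

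**5. The −3.6 against noise.** With over-dispersed counts, completer mean about 43 and shape 2 or 1, the SD is √(43 + 43²/2) = 31 or √(43 + 43²) = 43. With about 35 and 41 completers (60% and 70% of 58), SE = SD × √(1/35 + 1/41) = SD × 0.230, or about 7 to 10. So −3.6 is about 0.4 to 0.5 SE.

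**The case against.** Much of the case for leaving the plan alone is sound.

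- A reader might infer that the primary result is biased. The documents do not support that: everyone randomised is analysed as assigned, and the survey condition is inert with complete logs.
- A reader might take the earlier trials' retention ("Both studies observed poor retention (~40% loss-to-follow-up") as a forecast that 0.40 × 116, or about 46 people, will be dropped. The same sentence names lack of transportation as a major contributor, and those were face-to-face programmes. Here contact is virtual, reminders go out by call and text, and the survey and full completion are paid (Sections 5.2, 11.4 and 22.1).
- A reader might treat −3.6 as an expected error that exceeds the design difference. It depends on assumed differential completion, and 3.15 is calibrated to Poisson variance. Under over-dispersion, for which the plan prespecifies negative binomial regression, −3.6 is about half a standard error or less.
- Unequal completion would be visible, because survey completion is itself a secondary endpoint (Section 3.2) and participants with and without missing data will be compared.
- A logged zero is not always certain non-use. The app works offline after download (Section 2.3), and linkage relies on an ID the participant enters. The number of unlogged days is unknown and may be small.

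These points limit the harm. They do not give the completer analysis a purpose. It removes the people to whom non-use is assigned, but for those with full logs that non-use is recorded, so nothing assumed is tested.

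**Conclusion.** The point holds as a cheap improvement to the sensitivity analysis, not as a flaw in the main estimate. That the completer analysis drops observed totals and leaves unlogged days untested follows from the text, for participants whose logging continued. That completion tracks engagement is a reasonable inference which the documents do not state.

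If completion and its link to use are the same in both arms, the cost is lost precision and a subset of heavier users. If either differs, the completer difference can be wrong by several launches in the assumed scenarios, though that is small against over-dispersed noise at this sample size. How much the unlogged days matter cannot be sized from the documents.

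**What to change.** In Section 15.1:

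1. Compute the five-week launch total from the Smokefree.gov log for every randomised participant, whether or not the survey was completed, and delete the survey condition.
2. Define missing primary data only as days with no log available, for example after a withdrawal that ends data collection. State in Section 12.2 whether log transfer stops at withdrawal.
3. Make the main sensitivity analysis an all-randomised comparison that varies only those days. One end is zero use, which is the primary rule. The other is use continuing at the observed rate, fitted with log(days observed) as an offset. Participants with no observed days have no defined offset and should be kept at zero.
4. State that the offset result is one bound and not the answer. It assumes the earlier launch rate continues, so it is likely an upper bound if use declines over time.
5. Keep the completer analysis, if at all, as descriptive only.

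The cost is a few sentences and one extra model, with no new data and no change to the 116. The completer result no longer serves as the robustness check. If few days are unlogged, the two ends will nearly coincide, which is itself worth reporting.

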NCI's QuitGuide is a publicly available smartphone app for cessation. QuitGuide follows US Clinical Practice Guidelines which are the gold-standard in cessation treatment.²⁰ Guidelines call for tracking smoking status, offering quit planning, pharmacotherapy advice, tools to enhance motivation, and social support.²⁰ QuitGuide allows the user to track mood and cravings any time of the day, provides motivational messages and quit tips, and includes GPS technology which allows the user to mark a location as a trigger and then the app sends the user an alert and quit tip if they approach the location. QuitGuide was downloaded >100,000 times from 2015-2018 (personal communication w/[name] at Smokefree.gov; Smokefree.gov is managed by the

MEDICAL PROTOCOL (HRP-590)**PROTOCOL TITLE: QuitGuide for American Indians: Aims 2 & 3****VERSION DATE: 11-16-2022**

National Cancer Institute and the QuitGuide is a Smokefree.gov product). In testing of mainly White smokers without providing pharmacotherapy, QuitGuide was viewed as feasible and potentially efficacious as 8% quit (non-biochemically verified).¹⁵ Although the QuitGuide's quit rate is lower than face-to-face studies that include pharmacotherapy,²¹⁻²³ the reach and therefore the absolute number of people quitting with QuitGuide is potentially far greater. Given prior studies like the aforementioned ANBL that observed numerically lower abstinence among AIs in the non-tailored versus culturally-tailored arm, **we hypothesize that the QuitGuide fails to maximize quitting among AIs, but can be improved if tailored.**

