3.0 Study Endpoints/Events/Outcomes

3.1 Primary Endpoint/Event/Outcome:

The primary endpoint, which was used for power and sample size is the frequency of app use during the 5-week period.

3.2 Secondary Endpoint(s)/Event(s)/Outcome(s):

Secondary endpoints:

- Frequency of app use during the 1st week post-randomization
- Frequency of interactions with various app features (e.g. quit tips, trigger list) over the 5 weeks
- Study accrual relative to recruitment goal
- Study attrition measured as percentage of randomized participants that complete the survey at 5 weeks
- Frequency of returning saliva sample by 2 weeks post the week 5 survey (i.e., 7 weeks post randomization)
- Following measures at 5 weeks via exit survey
 - Usability of App Design measured using System Usability scale (SUS)³⁴ Acceptability of overall app (i.e., how likely would you be to recommend the app) and various app components (e.g. quit tips, trigger list) measured as Likert-scale responses

Fit of app with culture measured as Likert-scale responses

Exploratory endpoints:

Following measures at 5 weeks via exit survey

- Number of 24-hour quit attempts over the over the 5 week period
- Self-reported 24-hour abstinence at time of exit survey
- Self-reported 7-day abstinence at time of exit survey
- Self-reported 30-day abstinence at time of exit survey
- Nicotine replacement therapy and pharmacotherapy (e.g. Chantix) use over the 5 week period
- Other behavioral support (e.g. in-person, quitline) for smoking cessation over the 5 week period

MEDICAL PROTOCOL (HRP-590)

PROTOCOL TITLE: QuitGuide for American Indians: Aims 2 & 3

VERSION DATE: 11-16-2022

- Saliva cotinine at 5 weeks for those with 7-day abstinence prior to this time point to biochemically confirm self-reported 7-day abstinence (saliva cotinine < 10 ng/mL)

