5.0 Procedures Involved

5.1 Study Design:

This is a two-arm randomized clinical trial of the tailored vs standard QuitGuide app conducted.

5.2 Study Procedures:

To test feasibility, acceptability, and preliminary efficacy of the tailored QuitGuide versus standard QuitGuide for smoking cessation among AI peoples.

1. **Telephone Screener:** We will recruit AI smokers interested in quitting. Individuals will be screened over the phone for eligibility.

MEDICAL PROTOCOL (HRP-590)

PROTOCOL TITLE: QuitGuide for American Indians: Aims 2 & 3

VERSION DATE: 11-16-2022

2. **Phone-Based Baseline Interview:** If eligible, then consent will be completed. Then, participants will complete a REDCap survey (titled Baseline Survey—see below for measures). Participants will be randomized to either the *Tailored QuitGuide app* or the *Standard QuitGuide app*. Participants will be provided instruction on how to download the app to their smartphone. Upon download, all participants will be asked to provide a unique participant app ID in the app.

Randomization: Participants will be randomized with equal probability to either a tailored version of the NCI QuitGuide or a standard version of the NCI QuitGuide. Randomization will be stratified by rural/urban clinic, male/female gender, and <50 years of age/50+ years of age. Randomization will be completed using permuted block randomization with random block sizes of 2 and 4. We anticipate no or minimal block effects in our data, and therefore, we will not account for block effects in our data analysis. The randomization schedules will be created in advance.

3. **App interaction:** Upon opening the app for the first time, participants will be asked to set a quit date. All participants will set their quit date for one week later to standardize pre- and post- quit times. If smoking relapse occurs, participants will be provided the option to reset the quit date as this flexibility is permitted in the QuitGuide. Each participant will be asked to use the app for 5 weeks. Participants will have the option to contact the research coordinator at any time to report issues. At week 4, participants will be mailed a letter reminding them of the exit survey and will provide routine saliva sample collection kit with instructions to provide the sample on the same day of their exit survey, and materials (e.g., pre-paid envelope) to return the sample to the University of Minnesota for analysis.

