Measures of the ability to abstain from smoking (self-reported 24-hour, 7-day and 30-day abstinence) will be analyzed using a similar approach to the primary and secondary/exploratory endpoints, and summarized using a binary endpoint. Continuous 7-day biochemically-verified abstinence (saliva cotinine < 10 ng/mL⁸) will be summarized for those who self-reported 7-day abstinence prior to the week 5 survey, and analyzed using logistic regression, with a main effect for treatment group and adjustment of the stratification factors (rural/urban clinic, male/female gender and <50 years of age/50+ years of age). Because traditional tobacco (depending on the method of use and plants used) and secondhand smoke can increase saliva cotinine, additional analyses may be performed to explore their impact on biochemically-confirmed abstinence. In addition, secondary analyses will consist of an adjusted analysis, as described in above.

Subgroup Analysis

No subgroup analyses will be performed due to small sample size.

Missing Data

An intent-to-treat analysis requires that subjects are analyzed according to their randomized treatment assignment, regardless of compliance to the study product, and that complete data are available on all study subjects. Every effort will be made to limit the amount of missing data in this trial, and study participants will be incentivized to partake in each study component, return the saliva sample, and complete all components.

We will compare subjects with and without missing data in order to identify baseline covariates associated with missing data. All observed data will be utilized in the analyses, with missing data being assumed to be missing at random. Sensitivity analyses of the secondary/exploratory endpoints using multiple imputation may be considered depending on the amount of missingness.

Interim Analyses

No planned interim analyses.

All statistical analyses will be performed by [name] from the Masonic Cancer Center, Biostatistics Core.

15.2 Power Analysis:

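### Abstinence endpoints are to be modelled by four-term logistic regression with no sparse-data method, the denominator for verified abstinence is unclear, and the 30-day window does not fit the schedule

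*Combined protocol and SAP*

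**What the plan says.** Section 1.1 names preliminary efficacy as a purpose. Section 3.2 lists the abstinence outcomes as exploratory, among them "Self-reported 30-day abstinence at time of exit survey".

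Section 15.1 covers self-reported abstinence: "Measures of the ability to abstain from smoking (self-reported 24-hour, 7-day and 30-day abstinence) will be analyzed using a similar approach" to the primary and other endpoints, as a binary outcome adjusted for the three stratification factors (rural or urban, gender, age group). Cotinine-verified 7-day abstinence is "analyzed using logistic regression, with a main effect for treatment group and adjustment of the stratification factors". The same sentence says that this outcome is summarised for participants who reported 7-day abstinence. A further model with extra baseline covariates is also foreseen.

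The primary count analysis has named fallbacks for over-dispersion and excess zeros. The abstinence analyses have none, and Fisher's exact test is mentioned only for baseline comparisons.

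The only quit rate given for this app is in Section 2.2: "QuitGuide was viewed as feasible and potentially efficacious as 8% quit (non-biochemically verified"). On timing, Section 5.2 says: "All participants will set their quit date for one week later to standardize pre- and post- quit times". The survey link goes out at 5 weeks + 1 day.

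**The concern.** A logistic model with treatment and three binary factors has four slopes. If an arm or a stratum has no abstainers, maximum likelihood gives no finite estimate for that slope, yet software may still print a large coefficient and standard error. With few abstainers this is a practical possibility. Section 15.1 also states that the investigative team is not blinded, so a fallback that is not written down would be chosen by people who can see the results.

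Two further points affect what is estimated. Restricting the verified-abstinence model to self-reported abstainers conditions on something that happens after randomisation. And a 30-day window that is longer than the time since the scheduled quit date makes the result depend partly on when the survey is answered.

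**Working it through.** **The plan's own figure.** Section 15.2 plans "a total of 116 participants (n=58 in the tailored group and n=58 in the non-tailored group") to "achieve 80% power to detect a difference in frequency of app use between the groups of 3.15" against a control rate of 35, and Section 15.1 says "All statistical tests will be two-sided and a significance level of 0.05 will be used". For a two-sample Poisson test, n per arm = (1.960 + 0.842)² × (35 + 38.15) / 3.15² = 57.9, rounded up to 58. The figure is reproduced. It concerns app use only; the documents give no event count or power for abstinence.

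**Expected events.** Events = n per arm × (rate in control + rate in tailored). The rates are those quoted in Sections 2.2 and 2.3. The 40% loss is that of the two earlier face-to-face trials in Section 2.3; applying it here is an assumption.

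- 8% in both arms: 58 × 0.16 = 9.3; with 40% loss, 9.28 × 0.6 = 5.6.
- 7% vs 11%: 58 × 0.18 = 10.4; with loss, 6.3.
- 14% vs 23%: 58 × 0.37 = 21.5; with loss, 12.9.

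**Divergence.** The four-term model was simulated 3,000 times per scenario. Assumptions not in the documents: 50% rural, 50% women, 50% or 30% aged 50 or over, and factors unrelated to outcome.

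| Rates | Observed | Events | Events per term | Any slope diverges | Treatment slope diverges |
|---|---|---|---|---|---|
| 8% both | 116 | 9.3 | 2.3 | 6–9% | 1–2% |
| 8% both | 70 | 5.6 | 1.4 | 27–34% | about 10% |
| 7% vs 11% | 116 | 10.4 | 2.6 | 3–7% | about 2% |
| 7% vs 11% | 70 | 6.3 | 1.6 | 22–28% | 9–10% |
| 14% vs 23% | 116 | 21.5 | 5.4 | under 1% | 0% |
| 14% vs 23% | 70 | 12.9 | 3.2 | 1–2% | under 1% |

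A separate run at 8% gave 7.5% and 32% for any slope, and about 2% and 9% for treatment. If only 20% are rural, the any-slope figures at 8% rise to 22% and 48%; the treatment figures hardly move.

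**Check by formula.** The treatment slope diverges mainly when an arm has no events. The chance of this is 1 − (1 − 0.92ⁿ)². With n = 58 it is 1.6%; with n = 35 it is 10.5%. Both agree with the simulation.

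**Precision.** The median standard error of the treatment log odds ratio at 8% is 0.74 (116 observed) or 0.97 (70 observed). The 95% interval therefore runs a factor of exp(1.96 × 0.74) = 4.3 to exp(1.96 × 0.97) = 6.7 either side of the estimate.

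**Verified abstinence among self-reported abstainers only.** With 6 to 10 abstainers and an assumed 50% to 70% verifying, the four-term model has no finite solution in about 87% to 99% of simulated trials. With 22 abstainers the figure is 11% to 30%.

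**The 30-day window.** Taking first opening of the app as day 0, the quit date is day 7 and the survey link goes out on day 5 × 7 + 1 = 36. That leaves 36 − 7 = 29 days. The planned post-quit period is 35 − 7 = 28 days.

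**The case against.** The strongest reply is that the plan promises no abstinence rate. The 8% comes from one study of mainly White smokers, and the documents do not say which abstinence window it used. It cannot hold for all three windows at once: 24-hour abstinence should be at least as common as 7-day. At 23% vs 14%, divergence almost disappears, although that trial included pharmacotherapy. The 40% loss came from face-to-face trials where transport was a major cause; this trial is remote, with reminders and payments. All of this stands, so the event counts are conditional.

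A reader might infer that the treatment odds ratio will often be infinite and the efficacy signal unusable. The documents do not support that. At 8% it is mostly a stratification coefficient that diverges, and the treatment estimate usually stays finite. The endpoints are exploratory, the sample size rests on app use, and counts by arm can be reported whatever the model does. Nor does the remedy restore precision: at 8%, Firth estimation lowers the median standard error only from 0.74 to 0.67 with 116 observed, and from 0.96 to 0.84 with 70. Power at 58 per arm is about 11% for 11% vs 7% and 24% for 23% vs 14%.

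It is also fair that the self-reported endpoints are assigned an appropriate regression framework with diagnostics, so plain maximum likelihood is inferred. And Section 15.1 already limits the extra-covariate model for small samples, so removing that model would be a preference.

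On the 30-day endpoint, Section 11.4 also pays for surveys completed after 48 hours, so a scheduled quitter who answers late can reach 30 days. This shows that the endpoint is not impossible, but also that it depends on response time.

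**Conclusion.** The concern holds at a moderate level for exploratory endpoints. If 8% applies, expect about 9 events with full follow-up or 6 with 40% loss. Some coefficient then diverges in about 7% to 32% of trials, and the treatment coefficient in about 2% to 9%. These figures rest on the 8% rate, the borrowed loss rate and the assumed mix of strata; at about 21 events the problem nearly vanishes. Verified abstinence will be sparser than self-report by an amount that the documents do not give, so no specific verified rate should be read into the plan.

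The verified-abstinence denominator is the sharpest part. The restricted reading is possible, not certain. Under it, the model would nearly always fail at 6 to 10 abstainers, and at any number it would not compare the groups as randomised. The 30-day mismatch follows from the schedule itself and needs no assumed rate.

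**What to change.** Amend Section 15.1 as follows.

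- For every abstinence endpoint, use Firth-penalised (or exact) logistic regression with treatment and the three stratification factors. In a separate run at the 8% rate, Firth estimates stayed finite throughout.
- Report the number abstinent over the number analysed in each arm, and a risk difference with an exact or score confidence interval.
- Analyse verified abstinence by randomised arm. An event is self-reported 7-day abstinence with cotinine below the plan's 10 ng/mL limit. Participants who report smoking are non-events and stay in the denominator. State how participants without a survey or a saliva sample are handled.
- In Section 3.2, replace or supplement 30-day abstinence with abstinence since the originally set quit date (about 28 days). The original date must be specified because Section 5.2 lets participants reset it after relapse.

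The cost is a change of wording. Both methods are available in SAS and R, which the plan already names, and no new data are needed. Penalised estimates are slightly shrunk, and the wide intervals that come from the sample size remain.
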